## 8.8.5 Summary of Vital Signs

Vital signs (heart rate, BP, and body temperature) for Experimental Sessions will be summarized using descriptive statistics in tabular format listing values at pre-IP, prior to the supplemental dose, and at the end of each Experimental Session. Change from Baseline in vital signs will be presented.

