		,	Treatmen	nt 1				Treatmer	nt 2			Treat	ment 3		Primary Outcome	Study Termi- nation
Visit	V5	V6	V7	V8	V9	V10	V11	V12	V13	V14	V15	V16	V17	V18	V19	V20
Visit Description	Exp. 1	Int. 1.1	Int. 1.2	CAPS-5 T2: Tele- medicine	Int. 1.3	Exp. 2	Int. 2.1	Int. 2.2	CAPS-5 T3: Tele- medicine	Int. 2.3	Exp. 3	Int. 3.1	Int. 3.2	Int. 3.3	CAPS-5 T4 Outcome: Tele- medicine ^H	Study Termi- nation
Visit Timing	Within 1 wk of V3	Morn- ing after V5	Within 2 wks of V5	Within 3 weeks after V5	1-7 days before V10	Within 4 wks of V5 (+/-1 wk)	Morn- ing after V10	Within 2 wks of V10	Within 3 weeks after V10	1-7 days before V15	Within 4 wks of V10 (+/-1 wk)	Morn- ing after V15	Within 2 wks of V15	Within 4 wks of V15	8 wks post V15 (+/-2 wk)	2 days post V19 (- 1/+7 days)
Past/Current Medication &	✓	√	✓		✓	√	√	✓		√	✓	√	√	√		✓
Adherence																
Drug Screen	✓					√					✓					
Pregnancy Screen	✓					✓					✓					
Record	✓	✓	✓	✓	✓	✓	✓	✓	✓	✓	✓	\	✓	✓	✓	
All AEs C	✓	✓	✓		✓	✓	✓	✓		✓	✓	\	✓	✓		✓
Container Assignment ^D	✓					✓					✓					
Administer IP	✓					✓					✓					
8-hour Exp. Session	✓					✓					✓					
BP, Pulse, Temperature ^E	✓					✓					✓					✓ F
Overnight Stay I	✓					✓					✓					
90-min Integrative Session		✓	✓		✓		✓	✓		✓		✓	✓	✓		
Phone Call Follow-up ^G		√					✓					√				
Weight																√

C All Adverse Events (AEs) includes collecting Serious Adverse Events, AEs of Special Interest, AEs of Psychiatric Status, AEs requiring medical advice or attention, AEs that indicate withdrawal of a participant, and all other AEs
D Obtain container assignment 24 to 48 hours prior to each Experimental Session

E During Experimental Sessions, vitals are measured before Investigational Product administration, immediately before the supplemental dose is administered (or would be, if supplemental dose not given), and approximately 8 hours after initial dose, and as needed

F At Study Termination, only blood pressure needs to be measured
G 4 days of phone call follow-up: Day 2 and 7 after the Experimental Session, with two additional calls in between

H All visits must be scheduled to ensure that the Primary Outcome CAPS-5 T4 assessment is within the overall window provided: 18 weeks (+/-3 weeks) post V3

¹ See Appendix A for exceptions to overnight stay directive

Table 6: Time and Events – Study Measures

				Baseline & Treatment 1 Enrollment Confirmation				ment 1		Treatment 2				Treatment 3			Follow-up & Study Termination	

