8.3.1 Experimental Sessions

There will be three open-label Experimental Sessions (Visits 5, 10, 15). Procedures for MDMA-assisted psychotherapy will remain the same across all sessions and all procedures regardless of

dose received. Experimental Sessions must be at least 8 hours long, measured from 30 minutes prior to IP administration.

Experimental Session 1 (Visit 5) will occur within 1 week of the Baseline CAPS-5 (Visit 3) assessment. If the Baseline CAPS-5 assessment is completed outside of the allowed window, the investigator should consult the CRA and Medical Monitor to determine if the assessment should be repeated. The first Experimental Session will include 80 mg of IP followed by a supplemental half-dose 1.5 to 2 hours after the initial dose unless contraindicated.

MP16 Protocol

- Experimental Session 2 (Visit 10) will occur within 3 to 5 weeks of Experimental Session 1 (Visit 5) and after Integrative Session 1.3. A dose of 80 or 120 mg MDMA will be administered. A supplemental half-dose will be administered 1.5 to 2 hours after the initial dose unless contraindicated.
- Experimental Session 3 (Visit 15) will occur within 3 to 5 weeks of the second Experimental Session (Visit 10) and after Integrative Session 2.3. A dose of 80 or 120 mg MDMA will be administered. A supplemental half-dose will be administered 1.5 to 2 hours after the initial dose unless contraindicated.

Table 7: Schedule of	f Procedures	s for Experimenta	l Sessions
----------------------	--------------	-------------------	-------------------

Approximate Time	Procedure or Action
9:30	Urine drug screen and pregnancy test, concomitant medication
	information collected, participant acclimated to environment, C-SSRS
9:55	Baseline BP, body temperature, pulse
10:00	IP Administration, Begin video recording
11:30	BP, body temperature pulse
	Supplemental Dose Administration, unless contraindicated
17:30	C-SSRS, BP, body temperature, pulse

Pre-IP administration

- On the day of the Experimental Session, the participant will arrive approximately 30 to 60 minutes prior to IP administration.
- The site team will ensure the participant has not used caffeine or nicotine 2 hours prior, and fasted for 10 hours prior to IP administration and complied with all other requirements per Section 4.3 Lifestyle Modifications.

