10.2.3.1 Thermoregulatory Risks and Mitigation

MDMA administered in a controlled setting produces only a slight increase in body temperature [114]. Ambient temperature does not enhance or attenuate this slight elevation in humans. In data gathered from sponsor-supported Phase 2 studies, it was found that compared to placebo, a higher percentage of participants receiving MDMA had peak body temperatures greater than 1 degree Celsius (° C) above Baseline. However, there was no strong relationship between dose of MDMA and peak body temperature or between MDMA dose and elevation above threshold of 1° C above Baseline.

Ambient temperature will be kept at a comfortable level during Experimental Sessions. If a participant's temperature rises more than 1° C or the participant states that they feel hot, attempts will be made to decrease body temperature and increase comfort by removing blankets and layers of clothing, decreasing the ambient temperature, and, if necessary, directing a fan toward the participant. If at any time the temperature rises more than 1.5° C above Baseline despite these efforts, the site physician will be consulted for further evaluation and treatment.

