14.1.2 Safety Analyses

Safety data will be summarized by exposure to IP, unsolicited AEs, concomitant medications, suicidal ideation and behavior, and vital signs overall. If a participant has more than one AE mapped to the same PT, that AE will be reported once using the highest severity. AEs that occur on Day 0 (Experimental Session), Day 1, Day 2 after IP administration will be presented separately. Report incidence of AEs during Experimental Sessions such as clinical signs and symptoms, such as chest pain, shortness of breath, or neurological symptoms or any other signs or symptoms that may be indicative of a medical complication of the IP.

Frequency and incidence of concomitant medications will be displayed by generic name, sorted by class, and summarized by analysis set and category. Concomitant medications taken on Day 0 (Experimental Session), Day 1, Day 2 after IP administration will be presented separately. Any psychiatric concomitant medications will be tabulated by period (Preparatory, Treatment Period, Follow-up Period). Frequency and incidence of positive or serious ideation and suicidal behavior will be presented using descriptive statistics of C-SSRS scores in tabular format. Vital signs (heart rate, blood pressure, and body temperature) for Experimental Sessions will be summarized using descriptive statistics in tabular format listing values at pre-IP administration, prior to the supplemental dose, and at the end of each Experimental Session. Additional details are available in the Statistical Analysis Plan.

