## 3.3 Safety Objectives

The overall safety objective is to assess severity, incidence and frequency of AEs, AEs of Special Interest (AESIs), and Serious Adverse Events (SAEs), concomitant medication use, suicidal ideation and behavior, and vital signs to support the package insert for MDMA-assisted

psychotherapy. The following safety objectives will evaluate the safety of MDMA-assisted psychotherapy.

- Assess incidence of AEs during Experimental Sessions that may be indicative of a medical complication of the Investigational Product (IP), such as clinical signs and symptoms of chest pain, shortness of breath, or neurological symptoms or any other signs or symptoms that prompt additional vital sign measurements.
- Assess incidence of AEs by severity.
- Assess incidence of Treatment Emergent AEs (TEAEs) by severity.
- Assess incidence of TEAEs by severity taken during an Experimental Session and 2 days after IP administration.
- Assess incidence of AESIs, defined as AEs specified in the protocol related to cardiac function and abuse liability.
- Assess incidence of AEs by severity categorized as leading to discontinuation of IP, resulting in death or hospitalization, and continuing at Termination.
- Assess incidence of SAEs.
- Assess incidence of psychiatric concomitant medications taken during an Experimental Session and 2 days after IP administration.
- Assess incidence of any psychiatric concomitant medications taken during the Treatment Period.
- Assess incidence of serious suicidal ideation and positive suicidal behavior assessed with the Columbia Suicide Severity Rating Scale (C-SSRS). Assess mean changes in blood pressure, heart rate, and body temperature from pre-IP administration to end of each Experimental Session.

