#### 8.0 Analyses

Every effort will be made to ensure complete, accurate and timely data collection and to avoid missing data, to ensure the completeness of the data which can impact the integrity and accuracy of the final study analysis. The statistical analyses will be reported using summary tables, figures, and data listings. All analyses and tabulations will be performed using SAS® Version 9.4 or higher, and S-PLUS. In general, nominal variables will be described in terms of frequencies and percentages. Ordinal and non-normal continuous variables will be described using sample median and range.

Approximately normal variables will be described using sample mean and standard deviations and analyzed by parametric statistical tests. Except for the primary effectiveness analysis, all statistical tests will be two-sided and a difference resulting in a p-value of less than or equal to 0.05 will be considered statistically significant. All p-values will be rounded to and displayed in four decimals. If a p-value less than 0.0001 occurs it will be shown in tables as <0.0001. Data not subject to analysis according to this plan will not appear in any tables or graphs, but will be included in the data listings. Selected results may be presented graphically using standard graphical software.

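### Session vital signs are tabulated only at three scheduled times: as-needed readings have no planned analysis, rises above 1 °C and 1.5 °C are not counted, and the reference for change is unclear

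*SAP*

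**What the plan says.** SAP 8.8.5 plans descriptive statistics for session heart rate, blood pressure and temperature, "listing values at pre-IP, prior to the supplemental dose, and at the end of each Experimental Session", and adds that change from Baseline will be shown. Protocol 14.1.2 matches it: "listing values at pre-IP administration, prior to the supplemental dose, and at the end of each Experimental Session". The objective these tables serve is in SAP 3.3: "Assess mean changes in blood pressure, heart rate, and body temperature from pre-IP administration to end of each Experimental Session".

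Collection is wider than the table. Footnote E to Table 5 of the protocol (section 8.0) has readings before dosing, before the supplemental dose, "and approximately 8 hours after initial dose, and as needed". Table 7 in Protocol 8.3.1 puts the last scheduled set at 17:30: "C-SSRS, BP, body temperature, pulse". Protocol 10.2.2.1 ties extra measurements to clinical signs such as chest pain, breathlessness or neurological deficit. SAP 8.0 says of data that the plan does not analyse that they "will not appear in any tables or graphs, but will be included in the data listings".

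Protocol 10.2.3.1 sets two action levels for temperature. A rise of more than 1 °C leads to cooling measures. The second level is worded "If at any time the temperature rises more than 1.5° C above Baseline despite these efforts", and it leads to consultation with the site physician. The same section reports that in the sponsor's Phase 2 studies, compared with placebo, "a higher percentage of participants receiving MDMA had peak body temperatures greater than 1 degree Celsius" above Baseline.

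**The concern.** Readings prompted by a clinical sign bear on safety more directly than most, yet they have no place in the planned tables. The protocol's own temperature levels are written for any time in the session, and its summary of the Phase 2 experience is a percentage based on peaks. The planned tables give neither a peak nor a percentage. Vital signs are among the data meant to inform the package insert, so a reader of the study report would reasonably ask how many participants went above 1 °C or 1.5 °C. The planned tables would not answer that.

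A second problem sits in the same paragraph of the SAP. Change from Baseline has no clear meaning for a session reading, because SAP 8.4 defines Baseline in a way that does not match the objective.

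**Working it through.** The plan gives no figure to reproduce. The check sets the texts side by side and adds simple counts.

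1. **Volume.** Up to 60 participants × 3 sessions = 180 sessions. Two scheduled post-dose readings per session give 180 × 2 = 360 post-dose values of each vital sign in the table.

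2. **Time with no scheduled reading.** Dosing is at about 10:00 and the second reading is 1.5 to 2 h later. The last is at 17:30 (7.5 h) by Table 7, or at about 8 h by Table 5.
   - Shortest gap: 7.5 − 2 = 5.5 h.
   - Longest gap: 8 − 1.5 = 6.5 h.
   - On the Table 7 clock: 17:30 − 11:30 = 6.0 h.

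   Only as-needed readings can fall in this gap. If the supplemental dose has the same 1.25 to 2 h lag to peak that Protocol 2.2.2 gives for the initial dose (an assumption), its peak comes between 1.5 + 1.25 = 2.75 h and 2 + 2 = 4 h after the initial dose, inside the gap.

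3. **Sessions with a reading in no table.** The documents do not say how many as-needed readings to expect. Under assumed rates of sessions with at least one:
   - 2%: 0.02 × 180 = 3.6, about 4 sessions
   - 10%: 0.10 × 180 = 18 sessions
   - 20%: 0.20 × 180 = 36 sessions

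4. **What the planned table can answer.** Descriptive data in SAP 1.0 include the minimum and maximum. If these are also given for change from the pre-dose value, the table shows whether anyone exceeded +1 °C or +1.5 °C at a scheduled time. A maximum change of 1 °C or less means that no one did at that time. A larger maximum shows at least one participant above 1 °C, but not how many. Because each time is summarised separately, the table also cannot give the number of participants or sessions above a level at any measured time.

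5. **The adverse event route.** Protocol 11.1 lets an abnormal sign be an adverse event, and events in sessions are tabulated (SAP 8.8.2, Protocol 14.1.2). Protocol 10.2.3.1 asks for cooling or a consultation at its two levels; it does not say that crossing them must be recorded as an event.

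6. **The reference value.** The objective uses the pre-dose value, and Protocol 8.3.1 calls the reading just before dosing Baseline. SAP 8.4 takes Baseline from the Baseline visits for most measures, and from Screening for resting blood pressure. Table 5 schedules no vital signs at Visits 3 or 4. Read literally, session blood pressure would be compared with Screening, and pulse and temperature with visits that have no readings.

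**The case against.** The strongest reply is that nothing promised is missing. The objective is a mean change from pre-dose to session end, and the three times deliver it. Nowhere do the documents commit to a peak or threshold analysis. This stands.

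Events behind the extra readings are also covered. The first safety objective assesses adverse events in sessions, including signs or symptoms that lead to additional vital sign measurements, and Protocol 14.1.2 reports such events. This stands for the events; the measured values still have no planned summary.

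The second reading is well placed. It falls at 1.5 to 2 h, within the initial-dose peak of 1.25 to 2 h, and Protocol 5.5 expects the supplemental dose to add little to that physiological peak. It is a reasonable proxy for the peak, so the unscheduled gap should not be pressed hard. Extra readings would not close that gap systematically in any case.

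Finally, temperature is classed as a low-level risk, the site physician is given the vital signs before the supplemental dose, and SAP 9.0 has listings reviewed during the study. These protect participants during the study. They do not produce a summary for the report.

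**Conclusion.** The point holds as a gap in safety reporting that is cheap to close. It does not touch the primary effect estimate. As-needed readings have no planned analysis, and no table counts participants or sessions above the protocol's temperature levels. The wording on change from Baseline conflicts with SAP 8.4. Confidence is moderate: that as-needed readings go only to listings is inferred from SAP 8.0, since table shells are not among the documents, and the amount left out is unknown and may be small.

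A reader might infer more, and the documents do not support it:

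- That the vital-sign objective fails. It is met.
- That the plan leaves out the highest readings. Nothing shows that as-needed readings are the highest. Protocol 8.3.1 lets a session end once elevations have resolved, so some could be late rechecks with low values.
- That all rises go uncounted. Those recorded as adverse events are counted.
- That new tables would line up with the Phase 2 temperature result. Protocol 10.2.3.1 gives neither the percentage nor the reading schedule behind it, and this study has no placebo arm.

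**What to change.** In SAP 8.8.5 and Protocol 14.1.2, keep the three-time table and make these changes:

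- Define change as change from the same session's pre-dose value, for all vital signs.
- For each Experimental Session, summarise the maximum post-dose systolic and diastolic blood pressure, pulse and temperature over all scheduled and as-needed readings, with change from pre-dose and the number of post-dose readings.
- Give the number and percentage of participants (at most 60) and of sessions (at most 180) with temperature more than 1 °C and more than 1.5 °C above pre-dose.

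No count is proposed for blood pressure or pulse, because the protocol sets no in-session action level for them; 140/90 in the exclusion criteria is a screening level.

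The cost is SAP and protocol wording plus one or two tables from data already collected, with no added measurements. Sessions with more readings have more chances of a high maximum, which is why the number of readings is shown. Peaks that nobody measured stay unseen.

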#### 9.0 Timing of Analyses

Preliminary analyses and listing reviews will be ongoing throughout the studies to inform therapist supervision and assumptions made for upcoming Phase 3 trials. For clinical study

reports and publications, only locked database files will be used. The primary effectiveness analysis will be conducted after all participants complete Visit 20 and the database is locked.

